5.4.2 Secondary Analysis: SCCS with Pre- and Post-vaccination Control Intervals

The observation period will start on the first day of the pre-vaccination control interval and extend to day 90 after vaccination (day 0). The pre-vaccination control interval in the SCCS design will be defined as the interval with the same length as the risk interval (Table 3) ending 15 days prior to the date of the first (or, only) dose of the COVID-19 vaccination. The pre-exposure interval of 14 days will be excluded between the end of the control interval and exposure to vaccination to account for possible delay of vaccination following occurrence of an AESI.¹⁴ Sensitivity analyses will be conducted by using longer pre-exposure intervals, e.g., 28 days, and plotting incidence rates of the AESI by day prior to vaccination (Section 5.7.3.1). The post-vaccination control intervals will be defined the same as in the primary analysis (Section 5.4.1). Control intervals will be analyzed regardless of whether they are pre- or post-vaccination. Figure 2 presents some hypothetical cases in this design.

Figure 2. Hypothetical examples of SCCS design with pre- and post-vaccination control intervals for one-dose and two-dose vaccines

[figure not shown]

Note: The hypothetical risk interval following one dose is up to 28 days. However, the length of the risk and control intervals will vary for each AESI. The length of pre-vaccination control interval will vary based on the risk interval for each AESI and different analyses.

5.4.3 Exploratory Analysis: SCRI with a Pre-vaccination Control Interval

The observation period will start from the first day of the pre-vaccination control interval and extend through the end of the available risk interval, date of death, disenrollment, or the end of the study period, whichever comes first. The pre-vaccination control interval and pre-exposure interval will be defined the same as in the secondary analysis (Section 5.4.2). Figure 3 presents some hypothetical cases in this design.

Figure 3. Hypothetical examples of SCRI design with a pre-vaccination control interval for one-dose and two-dose vaccines

Note: The hypothetical risk interval following one dose is up to 28 days. However, the length of the risk and control intervals will vary for each AESI. The length of pre-vaccination control interval will vary based on the risk interval for each AESI and different analyses.

5.5 Study Population

Eligible vaccinees are persons who received at least one dose of the COVID-19 vaccine and met the following inclusion/exclusion criteria regardless of the occurrence of the AESI. All eligible vaccinees will be used for the attributable risk (AR) calculation.

The case population will consist of COVID-19-vaccinated individuals with the AESI. Incident AESI will be defined as the first recorded event for an individual during the study observation period if there are no claims for the same AESI in the preceding pre-defined clean window. The clean window will be anchored on the date of the AESI and will begin a pre-defined number of days prior to the AESI as specified in Table 3. Sensitivity analyses will be conducted with different lengths of clean windows to assess the robustness of the incident AESI definition (Sections 5.7.2.1 and 5.7.3.1).

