5.4.1 Primary Analysis: SCCS with Post-vaccination Control Intervals

The observation period will start from the vaccination date (day 0) of the first dose, if there are two doses, and extend to day 90. The post-vaccination control interval is defined as all follow-up time during the observation period following either the first or second COVID-19 vaccine dose (for two-dose COVID-19 vaccines) that is outside of the risk interval(s) until day 90 post-vaccination, end of study period, disenrollment, or death, whichever occurs first; while likely uncommon, this includes any time between the end of the first dose risk window and the receipt of a second dose. Figure 1 presents some hypothetical examples in design. Individuals who only accrued data during the risk intervals will be ineligible to be included in the analysis (Section 5.5.1).

Figure 1. Hypothetical examples of SCCS design with post-vaccination control intervals for one-dose and two-dose vaccines

[figure not shown]

Note: The hypothetical risk interval following one dose is up to 28 days. However, the length of the risk and control intervals will vary for each AESI.

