5.5.1 Primary Analysis: SCCS with Post-vaccination Control Intervals

Eligible vaccinees should meet the following inclusion/exclusion criteria.

Inclusion criteria:

- (i) Medicare beneficiaries enrolled in Part A (hospital insurance) and Part B (medical insurance) during the study observation period, as well as during the clean window prior to the occurrence of the AESI.
 - Continuous enrollment will be required from the start of an AESI's clean window relative to the occurrence of the AESI through day 90 post-vaccination, the end of the study period, disenrollment, or death, whichever comes first.
- (ii) Received at least one dose of a COVID-19 vaccine during the vaccination period of interest. The end of the vaccination period is defined as the vaccination cut-off date.
 - The vaccination cut-off date will be selected for each outcome to reduce the possibility of bias due to incomplete capture of events.
- (iii) For case population only, had a record of the AESI diagnosis during the study observation period.

Exclusion criteria:

- (i) Less than 65 years of age at the start of observation period.
- (ii) Does not contribute follow-up time to both risk and control intervals. If individuals disenroll, or reach the end of the study period during the risk window prior to accumulating any time for post-vaccination control intervals, they will be excluded.
- (iii) Had COVID-19 vaccination patterns that do not conform to expectations for the analysis of interest, e.g., doses that occur within a short time period following another dose or have a higher than expected dose number; more specific rules will be determined once more data on vaccination patterns are available.
- (iv) Had a diagnosis of the AESI during the AESI-specific clean window (Table 3) or during alternate clean windows assessed in sensitivity analyses.
- (v) Received different COVID-19 vaccines for the first and second dose. Based on the preliminary assessment, such a scenario only occurred in approximately 0.12% of cases with an AESI.

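### Clean window and enrollment look-back are counted from the AESI date, so AR non-cases have no anchor and, in the primary analysis, eligibility switches on during follow-up, lowering the RR slightly

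*Protocol*

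**What the plan says.** Section 5.5 defines incidence by looking back from the event: "The clean window will be anchored on the date of the AESI and will begin a pre-defined number of days prior to the AESI". Table 3 sets that window at 365 days for all four AESI. Inclusion (i) in section 5.5.1 uses the same anchor: "Continuous enrollment will be required from the start of an AESI's clean window relative to the occurrence of the AESI". Exclusion (iv) removes anyone with the AESI in that window. Of the inclusion criteria only (iii) is restricted to cases, and neither (i) nor (iv) carries such a label.

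Eligible vaccinees are those who "met the following inclusion/exclusion criteria regardless of the occurrence of the AESI", and "All eligible vaccinees will be used for the attributable risk (AR) calculation". Section 5.7.2 divides the excess cases by eligible vaccinations or dose-years.

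For the primary analysis, section 5.4.1 says: "The observation period will start from the vaccination date (day 0) of the first dose", running to day 90. Control time is post-dose time outside the risk intervals, so most of it comes after risk time. The conditional Poisson model in section 5.7.2 has interval length as its offset. Nothing delays a person's observation until the clean window has cleared.

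**The concern.** A criterion that uses the event date has a value only for people who have an event. The AR denominator consists almost entirely of people without one, and the protocol gives them no substitute index date. The denominator of a reported safety measure is therefore not defined by the stated rules.

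For cases, the anchor makes eligibility depend on when the event happens. For the same person, an event on day 5 may be rejected as not incident and an event on day 80 accepted. The person's early days stay in the model as risk time in which no event could have counted. In a design where risk time comes first, that removes events mainly from the risk interval and lowers the RR.

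**Working it through.** The protocol gives no figure for either effect, so there is none to reproduce. Table 6 is not affected and is used below only for scale.

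**1. AR denominator (no assumption needed for the gap itself).** Section 5.5 requires the criteria whether or not an AESI occurred. Criteria (i) and (iv) need an AESI date, and a non-case has none. If the rule is skipped for non-cases and a share q of those counted would have failed it, the denominator is too large by 1/(1-q), so the AR is multiplied by 1-q. This gives 0.99 at q = 1% and 0.95 at q = 5%. The value of q is an assumption.

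**2. Who is affected in the primary analysis.** With the last earlier AESI x days before day 0, the first day on which an event can be incident is 366 - x.

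| x (days before day 0) | First eligible day | Risk days blocked, of 28 |
|---|---|---|
| 360 | 6 | 5 |
| 340 | 26 | 25 |
| 320 | 46 | 28 |
| 300 | 66 | 28 |

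The band that clears during days 1 to 90 is about 275 to 365 days before day 0. An enrollment start in that band acts in the same way.

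**3. RR factor, primary analysis.** Let s be the affected persons' share of the baseline event hazard (an assumption), and let clearing days be uniform over 90 days. On day d a fraction (d-1)/90 of affected persons is eligible.

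- One dose, 28-day window: the mean over days 1-28 is 13.5/90 = 0.150; over days 29-90 it is 58.5/90 = 0.650.
- Two doses 21 days apart: days 1-49 give 24/90 = 0.267; days 50-90 give 69/90 = 0.767.

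The two means always differ by 45/90 = 0.5, so the result hardly depends on window length.

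Factor = [(1-s) + s × e_risk] / [(1-s) + s × e_control]. For one dose:

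- s = 1%: 0.9915/0.9965 = 0.995
- s = 2%: 0.9830/0.9930 = 0.990
- s = 4%: 0.9660/0.9860 = 0.980

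The loss is roughly s/2. A simulation check agreed within about 0.004.

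**4. Plausible s, prior-event route only.** Assume a yearly prior-event prevalence p and a recurrence rate k times baseline. The share of persons in the band is f = p × 90/365, and s = kf/(kf + 1 - f). With p of 0.2%, 0.5%, 1% or 2% and k of 1, 3, 5 or 10, s runs from 0.05% to 4.7% (factor 0.9998 to 0.976). Thirteen of the 16 combinations have s below 2%. The top value needs p = 2% and k = 10 together. The enrollment route would add to s by an amount that the protocol does not allow one to estimate.

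**5. The other two analyses.** In the SCRI, control time comes before risk time. For one dose and a 28-day window, control is days -42 to -15 and observation runs to day 28, which is 71 days. The eligible fractions are 13.5/71 = 0.190 in control time and 56.5/71 = 0.796 in risk time. The factor is 0.9980/0.9919 = 1.006 at s = 1% and 0.9796/0.9190 = 1.066 at s = 10%. In the secondary analysis at s = 10% it ranges from 0.986 (one dose, 28-day window) to 1.024 (two doses 28 days apart, 42-day window).

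**6. Scale.** At Table 6's minimum of 281 AMI cases, RR 1.42 and 28 of 91 days at risk, the expected share of cases in the risk interval is 1.42 × 28/(1.42 × 28 + 63) = 0.387. SE(log RR) = 1/√(281 × 0.387 × 0.613) = 0.12. A 1% shift is about 0.08 of that SE.

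**The case against.** Assigning an index date to non-cases is routine and could be left to an analysis plan. Looking back from the event gives every case the same 365-day definition of incidence, which matches section 4.3. The RR shift is small beside the sampling error at the planned minimum counts, and beside the claims-delay bias of up to 11% that section 5.3 accepts. Section 5.5 also commits to analyses with other clean-window lengths, and section 5.7.2.1 mentions a longer window over all available data that would largely remove the prior-event route.

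Much of this stands on size. It does not close the point. The protocol does more than omit an index date: it states an anchor that cannot be applied to people it says must satisfy the criteria. The all-data window is optional, is still built back from the event, and leaves the enrollment route and the AR gap untouched. The shorter 28-day AMI window in Table 4 moves the problem closer: an AMI in the 28 days before dose 1 clears during days 1-28, inside the AMI risk window.

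A reader might infer that every RR in the study is biased downward. That holds only for the primary analysis; the direction reverses in the SCRI and is mixed in the secondary analysis. A reader might also infer that AR numerator and denominator follow different eligibility rules. The protocol does not say so: it asks for one set of criteria and leaves non-cases without a way to be assessed against it.

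**Conclusion.** The point holds, and it is minor. The firmer part is the AR: as written, inclusion (i) and exclusion (iv) cannot be evaluated for non-cases. Its numerical effect is a factor of 1-q only if the rule is skipped for them, with q unknown.

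The RR part is a small downward pull in the primary analysis, with a factor of about 0.995 to 0.98 for assumed affected shares of 1% to 4%. It is probably about 1% or less, which corresponds to a share of up to 2%. That judgement rests on the assumed prevalence and recurrence ranges and on uniform clearing days; it does not quantify the enrollment route. Nothing in the protocol shows that a shift of this size would change a conclusion.

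**What to change.** In sections 5.5 and 5.5.1, anchor the clean window and the start of required enrollment on the first day of each analysis's observation period, for cases and non-cases alike. That is day 0 in the primary analysis, and the first day of the pre-vaccination control interval in the secondary and exploratory analyses. Take the first AESI from that day on as incident, and use the same anchor for the Table 4 windows. Eligibility is then fixed before follow-up starts, so e_risk = e_control and the RR factor is 1.000 for any s. One rule then serves both the cases and the AR denominator.

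The cost is a change of wording and the loss of a few late cases: those with an AESI or enrollment start about 275 to 365 days before the anchor day. The look-back before an event is also no longer exactly 365 days; in the primary analysis it would run from 365 to 365 + 90 = 455 days, depending on the event day.

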5.5.1 Primary Analysis: SCCS with Post-vaccination Control Intervals

Eligible vaccinees should meet the following inclusion/exclusion criteria.

Inclusion criteria:

- (i) Medicare beneficiaries enrolled in Part A (hospital insurance) and Part B (medical insurance) during the study observation period, as well as during the clean window prior to the occurrence of the AESI.
 - Continuous enrollment will be required from the start of an AESI's clean window relative to the occurrence of the AESI through day 90 post-vaccination, the end of the study period, disenrollment, or death, whichever comes first.
- (ii) Received at least one dose of a COVID-19 vaccine during the vaccination period of interest. The end of the vaccination period is defined as the vaccination cut-off date.
 - The vaccination cut-off date will be selected for each outcome to reduce the possibility of bias due to incomplete capture of events.
- (iii) For case population only, had a record of the AESI diagnosis during the study observation period.

Exclusion criteria:

- (i) Less than 65 years of age at the start of observation period.
- (ii) Does not contribute follow-up time to both risk and control intervals. If individuals disenroll, or reach the end of the study period during the risk window prior to accumulating any time for post-vaccination control intervals, they will be excluded.
- (iii) Had COVID-19 vaccination patterns that do not conform to expectations for the analysis of interest, e.g., doses that occur within a short time period following another dose or have a higher than expected dose number; more specific rules will be determined once more data on vaccination patterns are available.
- (iv) Had a diagnosis of the AESI during the AESI-specific clean window (Table 3) or during alternate clean windows assessed in sensitivity analyses.
- (v) Received different COVID-19 vaccines for the first and second dose. Based on the preliminary assessment, such a scenario only occurred in approximately 0.12% of cases with an AESI.

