2.1 Primary Analysis

Evaluate the risk of AMI, PE, DIC, and ITP after exposure to each COVID-19 vaccine using the self-controlled case series (SCCS) design. The primary analysis compares the risk of each event in a time

interval after vaccination (risk window) to that in time intervals post-vaccination after completion of the risk window (control window) within the study period.

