4.3 Safety outcomes: Adverse events of special interest (AESI)

Each of the AESI including AMI, PE, DIC, ITP will be assessed separately in the analysis by vaccine brand. The diagnosis of AESI will be identified with International Classification of Diseases, Tenth Revision, Clinical Modification (ICD-10-CM) codes (Appendix Table 1). The settings in which each outcome will be evaluated, as well as the clean (washout) and risk windows for each AESI are described in Table 3. The first occurrence of the event is defined as an incident AESI only if no event was recorded during the preceding pre-defined interval or the clean window. The risk window is defined as an interval post-vaccination during which occurrence of the AESI may be associated with the vaccine exposure. Both clean and risk windows are selected based on the literature and consultation with subject matter experts.

Table 3. AESI, settings, clean windows, and risk windows

AESI	Care Setting	Clean Window	Risk Window
Acute Myocardial Infarction (AMI)	IP	365 days*	1-28 days ^{4,5}
Pulmonary Embolism [#] (PE)	IP, OP/PB	365 days*	1-28 days ⁶⁻⁸
Disseminated Intravascular Coagulation (DIC)	IP, OP-ED	365 days*	1-28 days ⁹
Immune Thrombocytopenia (ITP)	IP, OP/PB	365 days*	1-42 days ^{10,11}

* Selection of clean window duration is based on clinician input.

[#] The PE onset date is determined by the date the PE code is reported in the database.

5 Study Design

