5.4 Definition of Risk and Control Intervals

The risk interval is defined as the time during which excess risk is hypothesized following each COVID-19 vaccine dose for the AESI based on biological plausibility and clinical input (Table 3). The selected risk intervals are AESI-specific and are determined based on review of literature and consultation with subject matter experts. Post-first dose risk intervals will run until the end of the interval, or until the person receives his/her second dose (if within the risk interval). Post-second dose risk intervals will run until the end of the risk interval.

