Pulmonary Embolism (PE)	IP, primary diagnosis position
Disseminated Intravascular Coagulation (DIC)	IP
Disseminated Intravascular Coagulation (DIC)	IP, primary diagnosis position
Immune Thrombocytopenia (ITP)	IP
Immune Thrombocytopenia (ITP)	IP, primary diagnosis position

To assess the robustness of risk and control intervals, different lengths of the risk interval and the control interval will be explored with clinical input and consideration of empirical data from temporal clustering by plotting the distribution of incident AESI since vaccination and temporal scans to detect statistical clustering of events post vaccination. Given the potential carry-over effect, we will exclude a range of periods (e.g., 7, 14, and 21 days) after the end of the risk interval from contributing to the control intervals.

To assess the robustness of the analysis to potential violation of the assumption that exposures are independent of outcomes (e.g. AESI post first-dose may delay or preclude administration of the second-dose), a modified SCCS analysis will be conducted which adjusts for censored, perturbed or curtailed post-event exposures.²²

To assess the robustness of the analysis to the potential violation of the assumption that observation time is independent of outcomes (e.g. death post-AESI censors follow up time), a modified SCCS analysis will be conducted which removes the independence assumption.²³

To assess the robustness of the analysis to the potential under-capture of second doses administered by providers who do not submit insurance claims, a sensitivity analysis will be conducted removing projected second-dose exposed time potentially misclassified as control time among patients with only one observed dose. The empirical distribution of exposed time post-second dose will be assessed among patients with two doses, and the corresponding time will be excluded from the control time of patients with only one observed dose.

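### For the two-dose brands, late first-dose recipients inform the primary rate ratio only if dose 2 was missed or delayed, which an AESI can cause; the vaccination cut-off should be set from the first-dose date and the dose spacing

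*Protocol*

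**What the plan says.** Protocol 2.1 places primary control time in "time intervals post-vaccination after completion of the risk window (control window) within the study period". Section 5.4 sets the risk intervals: "Post-first dose risk intervals will run until the end of the interval, or until the person receives his/her second dose", and "Post-second dose risk intervals will run until the end of the risk interval". Section 5.4.1 ends follow-up at day 90, study end, disenrollment or death, and counts any gap between the end of the dose-1 risk window and dose 2 as control time.

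Exclusion (ii) in 5.5.1 removes anyone who "Does not contribute follow-up time to both risk and control intervals" and spells out the case: "If individuals disenroll, or reach the end of the study period during the risk window prior to accumulating any time for post-vaccination control intervals". Inclusion (ii) in the same section adds a cut-off whose value is left open: "The vaccination cut-off date will be selected for each outcome to reduce the possibility of bias due to incomplete capture of events".

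Section 5.7.2.1 acknowledges that an "AESI post first-dose may delay or preclude administration of the second-dose" and plans a modified SCCS as a sensitivity analysis. For under-captured second doses, a second sensitivity analysis removes projected dose-2 risk time from the control time of people with one observed dose.

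**The concern.** Near study end, two people with the same first-dose date can differ in whether they carry any information, and what separates them is whether dose 2 arrived on time. The protocol itself says the outcome can change that. An event in the dose-1 risk window that stops or delays dose 2 keeps the person informative. The same event followed by an on-schedule dose 2 leaves the person with risk time only. Late accrual is thus enriched for dose-1 risk-window events, and the primary rate ratio for Pfizer-BioNTech and Moderna is pushed up even if there is no vaccine effect. Janssen has one dose and is not affected. At stake is a false or exaggerated excess in the primary test of a study meant to evaluate safety signals.

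**Working it through.** **Inputs.** Risk window W: 28 days for AMI, PE and DIC, 42 for ITP (Table 3). Dosing interval g: 21 days for Pfizer-BioNTech, 28 for Moderna (Table 2). Maximum follow-up: 90 days from dose 1 (5.4.1). F is the number of days from dose 1 to study end. Day 0 is not counted as control time, following 2.1.

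**The plan's own figures.** The protocol gives none for this effect. Its effect sizes are in Table 6. The signed-root likelihood-ratio SCCS formula gives 279 and 288 cases for AMI against the stated 281 and 286, so the table's AMI rate ratio of 1.42 is a fair yardstick.

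**Step 1: the bands.** With one dose, control time starts on day W+1. With dose 2 on day g, risk time runs to day g+W and control time starts on day g+W+1. The affected band is F from W+1 to g+W.

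| | Pfizer-BioNTech | Moderna |
|---|---|---|
| W = 28 | 29 to 21+28 = 49 | 29 to 28+28 = 56 |
| W = 42 (ITP) | 43 to 21+42 = 63 | 43 to 28+42 = 70 |

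**Step 2: rate ratio inside the band, true value 1.** Assumptions not in the documents: constant hazard; dose 2 exactly on schedule if given; probability of no dose 2 is q after an AESI that precedes it and s = 0.10 otherwise. Only one-dose people contribute. Days 1 to g-1 precede dose 2, so the expected rate ratio is [q(g-1) + s(W-g+1)] / (sW).

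- Pfizer-BioNTech, W = 28: (20q + 0.8)/2.8, which is 2.4, 3.9 and 6.0 at q = 0.3, 0.5 and 0.8.
- Moderna, W = 28: (27q + 0.1)/2.8, which is 2.9, 4.9 and 7.8.
- At q = s = 0.10 both give 2.8/2.8 = 1.

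**Step 3: pooled rate ratio.** Accrual is assumed uniform from December 11, 2020 to study end, with no earlier cut-off. The rate ratio ρ solves the expected score equation, the sum over groups of [A - (A+B)·ρR/(ρR+C)] = 0. A and B are expected events in risk and control time; R and C are risk and control days. W = 28, study end April 1, 2021:

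| | q = 0.3 | q = 0.5 | q = 0.8 |
|---|---|---|---|
| Pfizer-BioNTech, no dose-linked cut-off | 1.09 | 1.19 | 1.34 |
| Pfizer-BioNTech, F ≥ 50 for everyone | 1.07 | 1.14 | 1.26 |
| Moderna, no dose-linked cut-off | 1.18 | 1.38 | 1.72 |
| Moderna, F ≥ 57 for everyone | 1.13 | 1.27 | 1.52 |

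The avoidable part is 0.02-0.08 and 0.05-0.20. With study end May 31, 2021 it is about 0.01-0.03 and 0.02-0.09. On the log scale the April figures are about 5-17% (Pfizer-BioNTech) and 13-35% (Moderna) of log(1.42).

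**Step 4: what the cut-off leaves.** For Moderna at q = 0.5, log(1.27)/log(1.38) = 0.74, so about three quarters of the inflation remains. That remainder is event-dependent-exposure bias, present at any follow-up length.

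**The case against.** **The cut-off is still to be chosen.** This stands in part. A date that cleared the band would remove the problem, and operational dates are often fixed later, so the figures without a dose-linked cut-off are a scenario and not the plan. But the stated purpose is incomplete event capture, and the date is set per outcome although the margin needed differs by brand. Nothing ties it to dose timing. The study-end clause in exclusion (ii) does not prove that late vaccinees are expected. It is generic and would be needed under many cut-offs.

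**Exclusion (ii) is not the cause.** Correct. A reader might infer that deleting or narrowing it would cure the bias. In the conditional Poisson model a person with only risk time contributes a constant, so that edit leaves the rate ratio unchanged. The driver is event-dependent dose 2 under short follow-up.

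**The plan already has remedies.** Removing projected dose-2 time would strip days 29-49 or 29-56 from one-dose people, which empties the band. Under the Step 3 assumptions it gives 1.03, 1.06 and 1.11 for Pfizer-BioNTech and about 1.05, 1.11 and 1.19 for Moderna, closer to 1 than the cut-off achieves. The modified SCCS addresses the same assumption. Both are sensitivity analyses and leave the primary estimate and its test as they are.

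**Not only people without dose 2 are analysed.** Correct. A Moderna dose 2 on day 30 or later leaves a control gap, so the person stays informative. Spreading dose-2 dates lowers the within-band ratios but barely changes the pooled one.

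**The upper scenarios are extreme.** People who miss dose 2 because they die inside the risk window have no control time and drop out, so 80% is implausible for highly fatal events.

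**Conclusion.** The concern holds in limited form. The bands follow from the protocol's own rules, provided day 0 and the dose-2 day are not counted as control time, as 2.1 and 5.4 indicate. The direction is upward whenever an AESI lowers or delays dose-2 uptake, and the bias is zero if dose 2 is unrelated to the AESI.

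The size cannot be derived from the documents, which give neither dose-2 non-receipt nor an accrual pattern. Under the Step 2 and 3 assumptions the avoidable part is about 0.01-0.08 on the rate ratio for Pfizer-BioNTech and 0.02-0.20 for Moderna, and it shrinks as the share of vaccinees in the band falls. If only 15% are in the band and the rest have full follow-up, it is about 0.003-0.04 (baseline non-receipt 5-10%, cancellation of dose 2 by an AESI 10-50%).

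A reader might also infer that comparisons between brands are distorted. The protocol analyses each brand separately (4.3, 5.2) and plans no such comparison, so that is not part of the point.

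**What to change.** In 5.5.1, set the vaccination cut-off by brand and AESI on the first-dose date alone, whether or not dose 2 is recorded, so that dose 1 precedes study end by at least the dose spacing plus the Table 3 risk window plus 1 day. Take the spacing as a high percentile of the observed dose-2 spacing, with the Table 2 interval as the minimum. The minimum is then 50 days (Pfizer-BioNTech) and 57 (Moderna) with a 28-day window, and 64 and 71 for ITP. The percentile matters: a Pfizer-BioNTech dose 2 on day 25 extends risk time to day 53, beyond a 50-day margin.

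Run the 5.7.2.1 event-dependent-exposure analysis on the same population; the remaining bias belongs there. Exclusion (ii) needs no change for this purpose.

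The cost is a somewhat smaller case count, about 2-18% across the scenarios examined (2-13% in the 28-day, on-schedule runs) and somewhat more with a later percentile. On-schedule two-dose recipients in the band contribute nothing now, so their removal costs nothing.
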